**Compensation:** Per our prior standard in HIV/MMT counseling studies, clients will receive nominal compensation when attending each counseling session to offset transportation costs.

**Research interviews:** Participants in the enhanced usual care arm will complete a follow-up research assessment at 6 weeks post-baseline. Participants in the adapted FB arms will complete this assessment after the final FB session, also expected to be at approximately 6 weeks post-baseline. All participants will complete research assessments at 3, 6, and 12 months post-baseline. These follow-up assessments will assess the same domains as the baseline assessment and will specifically collect information on non-study psychiatric treatments in all arms, including both counseling and medications (both expected to be

extremely rare). Follow-up interviews will also repeat the MINI (all time points) to have a structured assessment of change in psychiatric diagnoses over time, as well as repeating the urine drug screen (6 months only) and Time Line Follow-Back alcohol and substance use assessment (all time points). Participants in all arms will receive standard financial compensation for their time after completing each research interview. All follow-up assessments will be conducted by trained research interviewers who are blinded to the participant's trial arm.

***Health care provider eligibility:*** Health care providers will also provide feedback on use of the adapted protocol. These participants will include a total of 10 different HIV and MMT care providers employed at the study clinics. The HIV/MMT care providers will be a mix of clinic staff delivering the intervention, HIV support service providers and other care providers that are determined to have meaningful involvement in the delivery of care for participating patients. These provider participants will complete semi-structured interviews at baseline, 6-weeks post enrollment, and at 3 months, 6 months, and 12 months to provide feedback on feasibility and acceptability of the adapted FB protocol.

**Outcomes, Measures and Data Collection.** The ***primary outcomes*** of the pilot trial will be the feasibility, acceptability, and fidelity of delivery of the adapted FB protocol. ***Secondary outcomes*** will include preliminary indicators of impact of the adapted FB protocol in improving HIV-related outcomes (eventual R01 primary outcomes) and MMT and mental health outcomes (eventual R01 secondary outcomes).

**Primary Outcomes:** *Feasibility* will be defined as the ability to successfully enroll and retain PLWH and OUD with CMDs in the pilot intervention. Feasibility will be evaluated by measuring the recruitment rate (number of patients approached to accrue the final sample). Additional indicators of feasibility will include study retention, defined as the ability to retain PLWH and OUD with CMDs in the pilot trial. Study retention will be evaluated by measuring the number of participants retained in the study (number of patients enrolled at baseline who are still enrolled in the trial), through study completion. An additional measure of intervention feasibility will be defined as the number of FB sessions attended by participants out of total FB sessions offered during the target intervention duration of 6 weeks.

*Acceptability* will be defined as the ability to deliver a culturally and resource-appropriate intervention. Acceptability will be assessed through brief exit interviews with all patient participants (n=75), HIV providers treating patients in the FB protocol, professional counselors (n=3), lay counselors (n=3), and supervising Master Trainers (n=1 per clinic, n=2 or 3 total). Exit interviews with patients will occur after the final FB session, while exit interviews with other groups will occur after the end of FB activities at each site. Exit interviews will include both closed and open-ended questions and will assess how easy the intervention was to participate in or deliver, the perceived usefulness of the intervention, and suggestions for improvement. The primary measure of acceptability will be overall participant satisfaction defined by the number of patients who were either very satisfied or somewhat satisfied with the FB among all participants who received the FB. Satisfaction will be measured on a 4-point Likert scale-- 1 indicates high satisfaction and 4 indicates high dissatisfaction.

*Fidelity* will be defined as adherence to the intervention protocol. Fidelity to session content for individual counseling sessions will be assessed by a Master Trainer by using a checklist of counseling session elements either during direct monitoring or using audio recording of up to 3 randomly chosen sessions per counselor. As we have defined in prior work, meeting or exceeding expectations at least 75% of checklist items during each

session will be considered fidelity to the intervention protocol.

**Secondary Outcomes:** Secondary outcomes will be used to provide preliminary information about effectiveness, taking into consideration the limited sample size for the pilot project. *HIV-related outcomes* (the primary outcomes for the eventual full-scale trial) will be defined as (a) *viral suppression at 6 months*, and (b) HIV appointment adherence between baseline and 12 months of follow up. Viral load will be captured from clinical records, or ordered by the study if no viral load is collected in the appropriate window. HIV appointment attendance will be evaluated by measuring the proportion of scheduled visits in the 12-month follow-up period that are attended vs. no-shows (the “kept visit proportion”), with no show defined as no appointment kept in the 30 days following a scheduled appointment. HIV appointment data will be abstracted from clinic records at the end of the study period.

*Mental health outcomes* (the secondary outcomes for the eventual full-scale trial) will be defined as DASS-21 total score indicating any CMD symptoms as well as mean subgroup scores for depression, anxiety, and stress at 6 weeks after enrollment (FB: treatment exit) across all study arms. We will consider both the simple severity level at follow-up as well as the absolute reduction in symptoms from baseline.

*Methadone maintenance engagement* (another secondary outcome for the full trial) will be defined as the proportion of days with methadone maintenance therapy adherence measured from study baseline through 12 months of follow up.

**Additional (tertiary) outcomes:** Tertiary *HIV-related outcomes* will be defined as (a) viral suppression at 12 months and (b) consistent ART use over 12 months as confirmed by clinical records. Tertiary *mental health outcomes* will be defined as DASS-21 total score indicating any CMD symptoms as well as subgroup scores for depression, anxiety, and stress at 3 months, 6 months, and 12 months across all study arms. We will consider both the simple severity level at follow-up as well as the absolute reduction in symptoms from baseline.

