Lay counselors may prove effective in delivering FB to PLWH with OUD; indeed, in other work we have demonstrated the effectiveness of peer counselors in improving ART adherence in this population. That said, CMDs may prove more difficult to treat in a population with OUD than among primary care patients, requiring the higher skill level of professional counselors for FB to be effective with this key population. A number of health care professionals in Vietnam have training in counseling, and the MOH could invest in expanding this cadre if evidence suggests that the higher level of training is critical. However, if lay counselors are equally effective then their deployment would be less expensive.

Our **objective** is to complete a pilot randomized trial of 75 patients from 4 MMT clinics where we have worked successfully in the past. We will compare FB delivered by professional counselors and FB delivered by lay counselors vs. enhanced usual care to improve CMDs and HIV care outcomes among PLWH and OUD in Vietnam. This work will

generate critical data to inform a fully powered R01 trial. We **hypothesize** that adapted FB will be acceptable to patients and providers, prove feasible to integrate into MMT clinics, be delivered with fidelity, and demonstrate preliminary indications of impact with both counselor groups.

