protocol. Feedback from this review will inform the development of the next draft of the protocol. In steps 7 and 8, an interventionist will be trained and this second draft will be piloted with 5 eligible patients to further refine session content. The process will culminate with a final version of the adapted FB protocol that will be ready for formal evaluation in Aim 2 in a three-arm pilot study.

**AIM 2: To assess the feasibility, fidelity, and acceptability of the adapted FB as well as preliminary indicators of its impact in improving CMD and engagement in HIV care and drug use treatment via a small three-arm individually randomized trial, comparing FB by professional counselors to FB by lay counselors to enhanced usual care for PLWH and OUD with CMDs.**

**Study Design.** We will complete a pilot trial in which we will randomize 75 eligible patients to either the FB by a professional counselor (n=25), or FB by a lay counselor (n=25), or enhanced usual care (n=25). Patients will be enrolled from 4 MMT clinics under CDC Hanoi jurisdiction and with which we have previous successful collaborations. Patients meeting full eligibility criteria (see below) will be invited to provide written informed consent to participate in the study. As a pragmatic effectiveness trial, the purpose of the eventual R01 will be to compare the effectiveness of the adapted FB protocol delivered by a professional counselor and delivered by a lay counselor relative to enhanced usual care in improving HIV/MMT care engagement and outcomes (primary outcomes for the future trial). Therefore in this pilot, consenting participants will be individually randomized in the same way, to one of those three arms (described below).

[figure not shown]

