### **3.4 Sample Size**

A total of 75 patients will be enrolled over time, recruited over a three-month period in year 2.

We recognize that the purpose of a pilot trial with limited sample size is not to be fully powered to detect statistically significant differences on patient outcomes but rather to provide reasonably precise estimates of parameters such as acceptability and fidelity, as well as preliminary evidence of the likely magnitude of effect of the intervention on the outcomes planned for the later trial. Assuming 80% retention (consistent with our team's previous work in this population), our starting sample size of 50 intervention participants is sufficient to estimate parameters such as the proportion of participants rating the intervention as acceptable with a 95% confidence interval of  $\pm 10$ -15 percentage points, and parameters such as the proportion of FB sessions with acceptable fidelity with a 95% CI of  $\pm 6$ -8 percentage points. Our starting sample size of 25 participants in each arm, with 80% retention, is sufficient to estimate risk ratios of the effect of the intervention on outcomes that have 95% CIs that are two- to three-fold wide (e.g., RR=0.63; 95%CI = 0.38-1.00 for the presence of elevated symptoms), depending on various assumptions about outcome frequency. For comparison of effect sizes, we note that the 24-clinic cluster-randomized trial of the FB found effect sizes much stronger than this (adjusted risk ratios of 0.21 [0.15-0.29] for presence of any symptoms and 0.28 [0.22-0.34] for presence of depressive symptoms). Thus the sample size is adequate to achieve our aims.

IRB# 20-1689

Protocol v3.0 2023-10-01

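### Primary acceptability measure, its stated precision and session attendance pool the professional and lay FB arms, although the pilot was set up to compare the two cadres

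*Combined protocol and SAP*

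**What the plan says.** **Acceptability.** Section 3.0, Primary Outcomes, sets the primary measure as "overall participant satisfaction defined by the number of patients who were either very satisfied or somewhat satisfied with the FB among all participants", counting only recipients of FB. Enhanced usual care patients are outside the denominator, and there is no split between the professional and lay arms.

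**Attendance.** The same section defines an additional feasibility measure as sessions attended out of sessions offered, again over all FB participants together.

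**Precision.** Section 3.4 assumes 80% retention and states that "our starting sample size of 50 intervention participants is sufficient to estimate parameters such as the proportion of participants rating the intervention as acceptable"; the half-width it gives, at 95% confidence, is ±10-15 percentage points. For effects on patient outcomes it changes basis: "Our starting sample size of 25 participants in each arm, with 80% retention".

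**Analysis.** Section 4.0 assigns descriptive statistics to feasibility, acceptability and fidelity. Among these primary outcomes it plans a professional-versus-lay comparison for fidelity scores only. Effectiveness is estimated for each FB arm against enhanced usual care.

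**The question.** Aim 2 (section 2.2) assesses feasibility, fidelity and acceptability by means of a three-arm trial comparing professional delivery, lay delivery and enhanced usual care. Section 1.2 explains the two FB arms: this population may need professional skill, but lay counselors would cost less if they work equally well.

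**The concern.** The two FB arms differ by design in who delivers the sessions, and the later full-scale trial is meant to test each cadre against enhanced usual care. The pilot therefore has to inform a judgement about each cadre. A primary measure pooled over both cannot do that. It is an average weighted by arm size, and the same value can arise from two equal arms or from one good and one poor arm.

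The stated precision has the same limit. A planner who reads ±10-15 points in section 3.4 and then looks at satisfaction with lay counselors would be relying on a width that belongs to twice as many patients.

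**Working it through.** **Inputs**
- FB patients: 25 professional and 25 lay, 50 in total (sections 3.0 and 3.4).
- Retention: 80% (section 3.4). Pooled 50 × 0.8 = 40; per cadre 25 × 0.8 = 20.
- Confidence level: 95% two-sided, z = 1.96.
- Expected satisfaction: not given in the documents. Assumed range: 90%, 80%, 50%.

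**Step 1: reproduce the plan's figure.** Normal-approximation half-width = 1.96 × √(p(1−p)/n) with n = 40:
- p = 0.9: 1.96 × √(0.09/40) = 9.3 points
- p = 0.8: 1.96 × √(0.16/40) = 12.4 points
- p = 0.5: 1.96 × √(0.25/40) = 15.5 points

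This matches ±10-15, so the stated precision is the pooled one and its arithmetic is sound.

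**Step 2: the same quantity per cadre.** Halving n widens the normal-approximation interval by √2. At n = 20 and high proportions that approximation is poor (p = 0.9 means two dissatisfied patients), so the Wilson half-width is the better guide:

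z × √(p(1−p)/n + z²/(4n²)) / (1 + z²/n)

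For example, with n = 20 and p = 0.9: 1.96 × √(0.0045 + 0.0024) / 1.192 = 13.7 points.

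| Basis | p = 0.9 | p = 0.8 | p = 0.5 |
|---|---|---|---|
| Pooled, n = 40, Wilson | 9.5 | 12.1 | 14.8 |
| Per cadre, n = 20, Wilson | 13.7 | 16.8 | 20.1 |
| Per cadre, n = 25, Wilson | 12.2 | 15.1 | 18.2 |
| Per cadre, n = 20, normal approximation | 13.1 | 17.5 | 21.9 |

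The n = 25 row is shown because the denominator is everyone who received FB and patients are asked after the final session, at about 6 weeks. Section 3.4 does not tie its 80% retention to that time.

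**Step 3: the difference between cadres.** With 20 per arm and equal proportions, the normal-approximation half-width is 1.96 × √(2p(1−p)/20). This gives 18.6 points at 90%, 24.8 at 80% and 31.0 at 50%.

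**Step 4: what pooling can hide.** These counts are hypothetical. Suppose 19/20 are satisfied with professional and 13/20 with lay counselors.
- Pooled: (19 + 13)/40 = 80%, ±12.4 points.
- Professional: 95%, Wilson 76% to 99%.
- Lay: 65%, Wilson 43% to 82%.
- Difference: 30 points. SE = √(0.95 × 0.05/20 + 0.65 × 0.35/20) = 0.117, so the 95% interval is 30 ± 23, about 7 to 53 points.

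Two arms at 16/20 each would give the same pooled 80%.

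**The case against.** The strongest reply is that the pooled measure matches the outcome as named. Sections 2.2 and 3.0 speak of the acceptability of the adapted FB protocol, meaning the intervention rather than the person delivering it. The analysis is descriptive, the arm is known for every patient, and nothing prevents a table by arm. No acceptability threshold or progression rule is stated, so no decision is shown to turn on the pooled number. Cadre-specific problems could also surface elsewhere: exit interviews with three professional and three lay counselors, repeated provider interviews, the fidelity comparison, and effectiveness by arm.

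Much of this stands. It shows that the split could be made, not that it is planned. Fidelity, a primary outcome of the same kind, has its cadre comparison written down. Patient satisfaction and attendance do not, and counselor interviews do not estimate either one.

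A reader might also infer more than the documents support:
- *That the protocol hypothesizes acceptability in each cadre.* In section 1.2 the words "demonstrate preliminary indications of impact with both counselor groups" attach most naturally to impact, while acceptability is tied to patients and providers. Section 2.1 says there are no specific hypotheses. The point rests on Aim 2 and the lay-versus-professional rationale.
- *That ±10-15 points is an error, or that the adequacy claim in section 3.4 rests on it.* The figure is right for the parameter it describes and is never applied to one cadre. The adequacy sentence closes the whole paragraph, directly after the risk-ratio discussion.
- *That a lay shortfall exists or is expected.* Nothing in the documents says so; the 95% and 65% split is only an illustration.

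**Conclusion.** The point holds as a mismatch between the question and the summary measure; it is not a numerical error. Acceptability and session attendance are specified only as pooled figures in a trial whose stated aim compares the cadres. Satisfaction in one cadre would be known to about ±14-20 points (Wilson, 20 patients, true proportion 90% to 50%), or about ±12-18 points with all 25, against ±10-15 pooled.

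These widths rest on the assumed satisfaction range, on 20 to 25 analysable patients per arm, and on treating patients as independent. With three counselors per cadre, satisfaction that varies by counselor would make the real uncertainty larger. The size of any difference between cadres is unknown.

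**What to change.** - **Section 3.0:** define satisfaction and session attendance separately for the professional and lay FB arms, and keep the pooled figure of each as a summary.
- **Section 4.0:** report satisfaction in each arm with a Wilson 95% interval. Report attendance in each arm with an interval that allows for clustering of sessions within patients. For both, give the professional-minus-lay difference with its interval. State that all of this is descriptive, with no hypothesis test.
- **Section 3.4:** keep ±10-15 points but label it as pooled over both FB arms. Add per-cadre Wilson precision of about ±14-20 points at 20 patients per arm (about ±12-18 if all 25 are analysed), and state the assumed proportions of 90% to 50%.

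The cost is wording only: no additional patients, visits or data items. The one drawback is that the stated precision per cadre looks less favourable than the pooled figure.

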### 3.1 Study Sites

The proposed study will be conducted at 4 public MMT clinics in the Hanoi, Vietnam area where we have successfully enrolled patients in prior studies. Each of the 4 health centers provides methadone maintenance treatment (MMT) to individuals with opioid use disorder as well as integrated HIV/ART care to those additionally living with HIV. Male users make up the vast majority of individuals with opioid use disorder here. In Vietnam, PLWH and OUD typically get integrated treatment with ART and methadone at district health centers. Thus, the co-location of HIV and MMT services makes these health centers ideal locations to serve PLWH with OUD. CMD screening and assessment are rare to nonexistent at HIV/MMT clinics in Hanoi, as in most clinical settings in Vietnam.

UNC Project in Vietnam will serve as the administrative home for the study and has longstanding relationships with all 4 proposed study sites, the Ministry of Health, and CDC Hanoi. Approximately 80 individuals living with HIV and with OUD present monthly at each site, providing adequate numbers for aim 2. UNC Project has previously successfully recruited and enrolled PLWH on MMT

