## 4.0 ANALYSIS

**Statistical Analysis.** Feasibility, acceptability, and fidelity will be evaluated using descriptive statistics. We will compare mean fidelity scores between the professional FB and lay FB counselors using an intent-to-treat approach, using a robust variance estimator to account for multiple observations per counselor. Means and proportions for HIV-related and mental health outcomes will be compared between arms using an intent-to-treat analysis approach.

We will evaluate effectiveness measures comparing professional counselors to enhanced usual care and lay counselors to enhanced usual care. Considering the purpose of this small pilot trial, our focus will be on estimating effect size and precision rather than statistical significance and hypothesis testing. To take advantage of the repeated-measures nature of the outcome data, we will also fit generalized estimating equation (GEE) regression models, using a link appropriate for each outcome (i.e. identity link for continuous variables and log link for binary variables), to simultaneously examine differences in outcomes at 6 weeks, 3 months, 6 months and 12 months between the arms. Given the relatively small sample size, it is possible that important predictors of outcome (such as baseline mental health symptom severity or time in HIV care) could end up being unbalanced between arms; if this is the case we will conduct secondary regression analyses adjusting for the unbalanced potential confounder.

In **secondary analyses**, we will examine whether HIV-related, MMT, and mental health outcomes vary by proportion of FB sessions attended and by number of elevated symptom domains at baseline (depression, anxiety, and/or post-traumatic stress).

In **moderation analyses**, we will explore whether severity of illness (duration; symptom severity; family history) modifies any preliminary evidence of efficacy in primary outcomes, while recognizing that a pilot trial is not designed to be powered to statistically test modification hypotheses.

**Missing data.** Every effort will be made to minimize missing data, including collecting detailed locator information for the participant as well as for up to three individuals who could help reach the participant should they drop out of contact. However, some missing

IRB# 20-1689

Protocol v3.0 2023-10-01

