## 7.0 WORKPLAN

**Timeline.** The Friendship Bench adaptation will be completed in year 1 quarter 3. The pre-pilot RCT to test materials and study procedures will begin in year 1 quarter 4 and will last 3 months. The 3-arm pilot study will begin in year 2 quarter 1, with recruitment completed

within a 3-month period. Given that MMT/ART patients attend clinic daily for directly observed MMT, we anticipate little difficulty fully enrolling within a 3-month period. However, we have enough leeway in our timeline to extend enrollment if needed to achieve our target sample size. Treatment will be completed by the middle of year 2, while research follow-up through 12 months will be completed by the middle of year 3. Feasibility and fidelity assessment will be ongoing throughout the trial, while patient acceptability assessments will be folded into the research outcome interviews. The remainder of year 3 will focus on data analysis and dissemination, manuscript preparation, and planning for the follow-up R01 RCT. We expect to generate a minimum of 3 manuscripts from this pilot study.

Activity	Year 1				Year 2				Year 3			
	Q1	Q2	Q3	Q4	Q1	Q2	Q3	Q4	Q1	Q2	Q3	Q4
IRB Regulatory												
Aim 1 - Adaptation to improve CMDs and engagement in PWID with HIV												
Adapt Friendship Bench; feedback; finalize												
Aim 2 Approach - Pilot study of Friendship Bench in PWID with HIV												
Prepilot followed by 3-arm pilot study recruitment: 3 months												
Pilot study treatment sessions: ~3 months w/ follow-up through 12 months												
Aim 2 Outcomes- Assessment of feasibility, acceptability, fidelity, and preliminary indicators of impact												
Feasibility, acceptability, fidelity measurement												
Preliminary indicators of impact: Research interview at 3, 6, and 12 months												
Dissemination												
Data analysis and dissemination, manuscript preparation, RCT planning												

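### The 30-day no-show rule lets one attended visit count for two HIV appointments, which inflates the kept-visit proportion if visits are 30 days or less apart

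*Combined protocol and SAP*

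**What the plan says.** Section 3.0 (Secondary Outcomes) makes HIV appointment adherence over 12 months one of two HIV-related secondary outcomes and describes that pair as "the primary outcomes for the eventual full-scale trial". It is measured as "the proportion of scheduled visits in the 12-month follow-up period that are attended vs. no-shows", with "no show defined as no appointment kept in the 30 days following a scheduled appointment". The source is the clinic record: "HIV appointment data will be abstracted from clinic records at the end of the study period".

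Section 4.0 adds only that "Means and proportions for HIV-related and mental health outcomes will be compared between arms using an intent-to-treat analysis approach". It gives no denominator rule for death, transfer or leaving care.

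The documents do not give the interval between HIV appointments. Section 3.1 says "Approximately 80 individuals living with HIV and with OUD present monthly at each site", but this describes patient volume in support of recruitment, not visit spacing. Section 7.0 says that "MMT/ART patients attend clinic daily for directly observed MMT", and Section 3.1 places HIV and methadone services in the same health centers.

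**The concern.** A 30-day window is a sensible allowance for late or rescheduled visits. It misbehaves when the next routine appointment falls inside it. A patient who misses one visit and keeps the next is then recorded as having kept both, so an isolated miss can never be a no-show.

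The pilot is meant to indicate the likely size of effect on outcomes planned for the later trial (Section 3.4), and Section 4.0 focuses on effect size and precision. A score pushed toward its ceiling would give a misleading control-arm level and, at moderate to high attendance, too small a difference between arms.

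Two further gaps belong to the same definition. The window refers to an appointment without repeating that it must be an HIV one, in clinics that patients visit daily. And only scheduled visits enter the denominator, so the score of a patient who leaves care depends on whether clinics go on booking visits.

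**Working it through.** The plan gives no expected rate, effect size or power for this outcome, so there is no stated figure to reproduce.

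**Inputs.** From Section 3.0: the kept-visit proportion, the 30-day window and 12 months of follow-up. Assumed, because not stated: the visit interval (28 days, 30 days, calendar-monthly, 31 days or more); independent attendance with probability p at each visit; and kept visits that are themselves scheduled HIV visits within the 12 months.

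**Formula.** If the next visit is no more than 30 days away, a scheduled visit is a no-show only if both it and the next are missed, so its expected score is 1 − (1 − p)². The last visit of the period has no later visit to rescue it and scores p. If the next visit is more than 30 days away, every visit scores p.

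**28-day spacing (13 visits).** Expected score = [12 × (1 − (1 − p)²) + p] / 13. For p = 0.5: (12 × 0.75 + 0.5)/13 = 73.1%. For p = 0.6: (12 × 0.84 + 0.6)/13 = 82.2%. For p = 0.8: (12 × 0.96 + 0.8)/13 = 94.8%.

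**30-day spacing (12 visits).** Expected score = [11 × (1 − (1 − p)²) + p] / 12, which gives 72.9%, 82.0% and 94.7% for the same p.

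**Same-date calendar-month booking (12 visits, January to December).** Only the gaps that start in February, April, June, September and November are 30 days or less: 5 of 12. Expected score = p + (5/12) × p(1 − p). For p = 0.5: 0.5 + 0.4167 × 0.25 = 60.4%. For p = 0.6: 70.0%. For p = 0.8: 86.7%.

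| True attendance | 28–30 days | Calendar month | 31 days or more |
|---|---|---|---|
| 50% | 73% | 60% | 50% |
| 60% | 82% | 70% | 60% |
| 70% | 89% | 79% | 70% |
| 80% | 95% | 87% | 80% |
| 80% minus 60% | about 13 points | about 17 points | 20 points |

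Ignoring the last visit, the difference at 28–30 days is 0.96 − 0.84 = 12 points.

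**Attending every second visit.** At 28 days, attending visits 2, 4, …, 12 is truly 6/13 = 46% and scores 12/13 = 92%; attending the odd visits is 7/13 = 54% and scores 100%. At 30 days, 6/12 = 50% scores 92% or 100%. With calendar-month booking, 2 or 3 of the 6 misses are rescued, giving 8/12 = 67% or 9/12 = 75%.

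**Leaving care.** The 30-day rule does not help a leaver: any visit booked after departure is a no-show. If booking continues, the score is the true proportion. If booking stops after one unkept visit, k attended visits score k/(k + 1). With 28-day visits, k = 1 scores 50% (true 1/13 = 8%), k = 3 scores 75% (3/13 = 23%) and k = 6 scores 86% (6/13 = 46%).

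**The case against.** **The interval is not stated.** The whole double-credit effect needs gaps of 30 days or less, and at longer gaps the rule is only a grace period. This stands. A reader might take the remark in Section 3.1 about people presenting monthly as evidence of monthly appointments. It is a count of patients per site, and Section 7.0 says they attend daily, so it does not establish visit spacing. Even true calendar-month booking produces only part of the effect.

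**Near-perfect scores for poor attenders and leavers.** A reader might infer that such patients generally score close to 100%. The documents do not support that. Scores of 92–100% need regular alternation at 28–30 days; random 50% attendance scores about 73% even there. For leavers, inflation needs the further unstated condition that booking stops, and early leavers would then score 50–75%.

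**Hidden differences between arms.** The same rule applies in every arm, so it creates no effect of its own. It shrinks the difference, and only when attendance is fairly high: ignoring the last visit, the multiplier on a true difference is 2 − p₁ − p₂, which is below 1 only when p₁ + p₂ exceeds 1. At 80% versus 60% it is 0.6. The difference is attenuated, not removed.

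**Limited consequence here.** The pilot's primary outcomes are feasibility, acceptability and fidelity. Viral suppression, consistent ART use and methadone adherence also bear on engagement. This lowers the urgency, but none of those outcomes corrects this one.

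**The methadone reading is literal.** The surrounding sentences concern HIV appointments, so the intended meaning is probably clear. The point is one missing word that an abstractor working from shared records would need.

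**Conclusion.** The concern holds as a conditional defect in the definition. As written, one attended visit may be credited to two appointments, and whether that distorts the outcome depends on a visit interval that the documents omit. Under random attendance, the inflation for true rates of 50–80% is about 15 to 23 points at 28–30 days, about 7 to 10 points with calendar-month booking, and nil at 31 days or more. A 20-point difference (80% versus 60%) becomes about 13, about 17 or 20 points respectively. These figures rest on independent attendance and on the assumed intervals; mixed intervals would fall in between.

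The leaving-care effect is separate and rests on booking practice that the documents do not describe, so it supports a sensitivity analysis and not a claim that the primary scoring is wrong. The change is worth making because the outcome is intended for the later trial and the repair is cheap, not because the pilot's main conclusions depend on it.

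**What to change.** In Section 3.0 (Secondary Outcomes), define a scheduled HIV appointment as kept only if an HIV visit is attended within 30 days of it and before the next scheduled HIV appointment, with each attended visit credited to one appointment. State the usual interval between HIV visits at the study clinics. Under this rule the alternate attender who missed the odd-numbered visits scores 6/13 = 46% at 28 days or 6/12 = 50% at 30 days, in place of 92% or 100%, and the allowance for late visits is retained.

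Add a sensitivity analysis for leaving care: go on counting expected visits at the patient's most recently documented interval until 12 months, death or transfer. Do not fix the denominator to the baseline schedule. A patient moved from monthly to quarterly visits at month 6 who keeps all 6 + 2 = 8 appointments would then score 8/12 = 67%.

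The cost is small. The same clinic records are abstracted at study end, with each patient's current visit interval recorded as well. Scores will be lower where visits are 30 days or less apart and, provided that only HIV visits were being credited, unchanged where visits are further apart.
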